5.3.4 Safety sample

The safety analysis sample includes all randomised participants exposed to at least one dose of randomised treatment.

6. ANALYSIS VARIABLES

Many of the study variables are measured at more than one visit (section 4.6 above). In the reporting of the analysis the latest timepoint will be taken to be most important. Usually this will be at 12 months.

The trial is powered on the outcome measure of body weight at 12 months. A p-value will be provided for this hypothesis test. For this and other outcomes 95% confidence intervals will be presented.

6.1. Primary outcome variable

Change from baseline in body weight at 12-month follow-up.

6.2. Clinical and anthropometric outcome variables

The secondary outcome measures are listed as follows according to the type of the variable (continuous, categorical) and the sample (full sample, mechanistic sub-sample). Each will be analysed at the 12-month principal timepoint of follow-up but may also be presented at earlier follow-up timepoints (2 and 6 months)

for the purpose of secondary analysis. These will be listed at a later point when justifying the analysis method to be used.

Sec	condary objectives	Variables (all in full sample)	Type of variable	Timepoint(s) of evaluation of endpoint
1.	To determine effects on glucose homeostasis as a surrogate marker of type-2 diabetes risk	Fasting biochemistry: -Glucose (mmol/L) -Insulin (mIU/L)	Continuous	6 and 12 months
2.	To determine effects on blood lipid and cholesterol as surrogate markers of CVD risk)	 Fasting biochemistry: Triglycerides (mmol/L) Total cholesterol (mmol/L) LDL cholesterol (mmol/L) HDL cholesterol (mmol/L) 	Continuous	6 and 12 months
3.	To determine effects on blood pressure as a surrogate marker of CVD and stroke risk	Blood pressure (mean of 3 measurements each): - SBP (mm/Hg) - DBP (mm/Hg)	Continuous	2, 6 and 12 months
4.	To compare changes in body weight/ waist/ BMI/body composition during the 12 months intervention	 Body weight Waist/hip BMI (kg/m²) Body composition: Fat mass/Total body fat (FM) (kg) Fat Mass Index (FMI) (kg/m²) Percent body fat (Fat%) (taken from Body Impedance machine) Fat free body mass (FFM) (kg) FM/FFM ratio 	Continuous	2, 6 and 12* months

* Body weight already included as primary outcome at 12 months

6.3. Lifestyle factors' variables

Lifestyle factors	Variables	Type of variable	Timepoint(s) of evaluation of endpoint
A. To compare changes in physical activity during the 12 months intervention	IPAQ (International Physical Activity Questionnaire) scores (all participants) - Low - Moderate - High	Categorical	2, 6 and 12 months
	Accelerometer data (Sub-study participants only): - total energy expenditure - active energy expenditure - average metabolic equivalent of tasks (METs) - physical activity duration - step count - duration on body - lying down - sleep duration	Continuous	Baseline and 12 months

	Lifestyle factors	Variables	Type of variable	Timepoint(s) of evaluation of endpoint
B.	To compare changes in other lifestyle factors during the 12 months intervention	 Smoking status (current/ex-smoker/never) Vaping status (current/ex-vaper/never) Drinking status (current/ex-drinker/never) Recreational substances status (yes/no) 	Categorical	2, 6 and 12 months
C.	To compare changes in diet during the 12 month intervention	Food diaries: -Energy (in kcal or kJ) -Protein (g) -Fat (g) -Carbohydrate (g) -Fibre (g)	Continuous	2, 6 and 12 months

6.4. Safety Variables

Adverse events will be classified by "type" (serious/non-serious), severity (mild, moderate, severe), causality/relationship to study treatment (unrelated, unlikely, possibly, probably, definitely), expectedness (expected vs unexpected, SAEs only), outcome (resolved, resolved with sequelae, persisting, worsened, fatal) and MedDRA Structure (system organ class (SOC), high level group term (HLGT), preferred term (PT), lowest level term (LLT)).

According to the safety reporting manual of iPREVENT the causality is made by the investigator responsible for the care of the participant and the expected adverse events of the trial are gastrointestinal symptoms. All important abnormal laboratory test results occurring during the trial will be recorded as adverse events. Pregnancies at any point during the trial will also be recorded.

6.5. Demographic Variables

The demographic variables collected and to be summarized in Table 1 of reports are age, gender and ethnicity.

Mechanistic sub-study objectives:		Variables	Type of variable	Timepoint(s) of evaluation of endpoint
a.	To compare changes in colonic metabolism to identify the relative abundance of the bacterial	Gut microbiota abundance (stool sample - metataxonomic analysis of the 16S rRNA gene)	Continuous	12 months (changes from baseline)
	component of the microbiome	Hydrogen breath test (ppm)	Continuous	
b.	(i) To analyse the metabolite profile (nuclear magnetic resonance spectroscopic analysis)	Level of SCFA and metabolites profile (stool sample) (propionate, acetate and butyrate)	Continuous	12 months (changes from baseline)
	(ii) To determine how these specific changes in the colonic environment influence L-cell differentiation	Count of L-cells in intestinal organoid	Continuous	

6.6. Mechanistic sub-sample variables

	Mechanistic sub-study objectives:	Variables	Type of variable	Timepoint(s) of evaluation of endpoint
c.	Appetite regulation:			
	(i) To compare subjective feelings of appetite	-Visual Analogue Scales (VAS) of appetite (4 scales: hunger; desire to eat; fullness; nausea)	Continuous	12 months (changes from baseline)
	(ii) To compare anorectic gut hormones	- PYY - GLP-1 - Gastrin - CCK	Continuous Continuous Continuous Continuous	
d.	Mechanisms involved in weight maintenance: (i)To compare energy expenditure (ii) To compare hepatic lipid metabolism	 Energy expenditure (kcal/day) Carbohydrate oxidation (g/min) Fat oxidation (g/min) RER (respiratory exchange ratio) Stable isotope tracers of fat 	Continuous Continuous Continuous Continuous Continuous	12 months (changes from baseline)
	(iii) To compare Total Body Water	oxidation (¹³ CO ₂ + ¹³ C-beta- hydroxybutyrate) -De Novo Lipogenesis (² H ₂ O) - ² H ₂ O in body water	Continuous	

6.7. Compliance variables

This is of interest in itself but it is also involved in the supplementary investigation as mentioned above.

Secondary objective:	Variable	Type of variable	Timepoint(s) of evaluation of endpoint
To determine compliance during the 12-month intervention	Accountability of returned used for all subjects.	Continuous	2, 6 and 12 months

7. STATISTICAL METHODOLOGY

7.1. General Methodology

7.1.1 Data decisions made

In principle the data manager will make limited decisions about data variables and values so that issues such as missing data can be comprehensively handled by the trial statistician. Decisions which impact on the analysis will be recorded in the final clinical study report.

7.1.2 Outcomes requiring derivation

The International physical activity questionnaire (IPAQ) short form asks about three types of activity undertaken in four domains: a) leisure time physical activity, b) domestic and gardening activities, c) work-related physical activity and d) transport-related physical activity. It provides separate scores on walking,

moderate-intensity and vigorous-intensity activity which are summarized using median and interquartile range values and expressed in MET-minutes/week (17). According to the IPAQ guideline, "METs are multiples of the resting metabolic rate and a MET-minute is computed by multiplying the MET score of an activity by the minutes performed". A combined total physical activity score is also reported and calculated from the summation of the duration in minutes and frequency (days) of walking, moderate-intensity and vigorous-intensity activities. In the current study, the categorical variable of IPAQ will be used, which describe the physical activity in three levels: Low, Moderate and High. The data cleaning and processing (including missing value guidance) of IPAQ will be followed according to the guideline(17).

7.13 Use of data transformation

It is anticipated that some continuous outcomes, mainly in the mechanistic sub-study, will need to be considered for transformation, such as the accelerometer data or measurements expressed as percentages. Assumptions of normality and constant variance required by the models will be examined using residual and other diagnostic plots. If it is relevant, such as when there is too much skewness for the sample size such as triglycerides, a log transformation will be considered, because this retains a sensible interpretation for inferences; in relative terms between arms. If an absolute interpretation is needed, then data transformation may not be undertaken, but a nonparametric Bootstrap method for obtaining confidence intervals may be considered (18).

7.1.4 Defining and handling outliers

Outliers are observations that have extreme values relative to other observations observed under the same conditions. An outlier will be defined and handled in two ways:

i) For the purpose of checking data at interim and final analyses (for querying), defined as data-points being at least three standard deviations away from the mean of its distribution of values (either cross-sectional, change from baseline, or pairs of successive serial data-points ('bivariate outliers') observed across other patients. These definitions will apply to the transformed scale for those outcomes that have been log transformed. If many outliers are identified in this way, other thresholds (eg. 3.5SD or 4SD) will be used for querying only those that may be more highly influential.

Outliers will be identified for further investigation by looking at the distributions of the data through histograms, scatter plots or box-plots. Univariate tests for the compatibility of the distribution with a normal distribution will not be undertaken since they can be too sensitive to departures that are often not relevant for the comparison of means (Central Limit Theorem).

Once an outlier is found, a blinded member of the team with enough clinical experience will be involved in the decisions as to whether a data value is impossible versus implausible versus plausible. If the outlier is impossible, then it will be set to missing. If an outlier is clinically plausible, the outlier will remain. If an outlier is in between these extremes, i.e. clinically implausible (but possible), it will not be ignored or deleted but will be retained for ITT analysis. If outliers remain in the distribution of a variable, then data transformations or nonparametric methods of analysis may be considered.

ii) For comparative analysis, outliers will be defined as observations with model residuals that are at least four standard deviations away from the mean of its distribution of values, considered 'potentially implausible'. In this situation, sensitivity analysis will be undertaken to check whether the outlier is influential by obtaining results primarily with and then without inclusion of the outlier. If the conclusions are changed, then this will be noted.

7.1.5 Flow diagram/recruitment

The flow diagram of the study is the one below. This will include the number assessed for eligibility, randomised, who comprise the intention to treat population, and the numbers followed-up to be in the analyses of the primary outcome as well as the main reasons for missing data by stages of the trial (CONSORT diagram(19)).

iPREVENT	STATISTICAL ANALYSIS PLAN	13 Jan 2
Screening: Consent, ECG, pressure, physical ad	body weight, height, waist, hip, body composition, BMI, full blood count, ctivity questionnaire (IPAQ), pregnancy test, lifestyle questions and medic history/medications	al
	270 eligible participants	
Baseline: Body weight, heig physical activity questionna Mechanistic evaluations (N=	ht, waist, hip, body composition, BMI, fasting blood test, blood pressure, ire (IPAQ), pregnancy test, lifestyle questions and medical history/medica 52): Energy expenditure, substrate oxidation, appetite regulation, hydrog breath tests, gut microbiota and accelerometer	food diary, tions, AEs. gen and ¹³ C
Inulin propion (IPE) 135 partici	RANDOMISATION (Minimisation by site, sex, participation in sub study, BMI within ethnicity) Placebo (inulin) 135 participants	
2 months: Body weight,	waist, hip, body composition, BMI, blood pressure, food diary, physical ac	tivity
questionnaire	(IPAQ), pregnancy test, lifestyle questions, medical history/medications, sachet count, AEs	
	\bigvee	
6 months: Body weight, w physical ac	vaist, hip, body composition, BMI, fasting blood test, blood pressure, food tivity questionnaire (IPAQ), pregnancy test, lifestyle questions, medical history/medications, sachet count, AEs	l diary,
V		_
Full sample: 202 subjects (12 months: Body weight, v physical activit history/medica	101 per arm) are expected to be followed up vaist, hip, body composition, BMI, fasting blood test, blood pressure, food y questionnaire (IPAQ), pregnancy test, lifestyle questions, medical tions, sachet count, AEs.	l diary,
Mechanistic sub-sample: 3 Evaluations: Energy exper	6 subjects (18 per arm) are expected to be followed up nditure, substrate oxidation, appetite regulation, hydrogen and ¹³ C breath gut microbiota and accelerometer	n tests,

7.1.6 Withdrawals/follow-up

Alongside the descriptions of the number/percentage of patients withdrawing from the study by arm in the CONSORT diagram as mentioned above, the number and percentage of patients withdrawing just from intervention (who continue data collection) will be summarized by treatment arm, reasons and timing. Baseline demographics, lifestyle factors and participants' weight will be described and compared between those withdrawing from the study and those completing the study using means (standard deviations (SD)) or number (percentages) and compared using difference in means or proportions with 95% confidence intervals.

7.1.7 Baseline demographics

Baseline descriptions of participants by treatment and overall will be summarised (into Table 1 of the report). No significance testing will be carried out as any differences found may be chance-generated and not for hypothesized reasons. This applies also for baseline in those in the mechanistic study, who consent to this prior to allocation to study arm.

7.2. Primary outcome analysis

7.2.1 Description

be included.

The primary outcome measure is the change from baseline in body weight at 12 months. As the analysis approach for continuous outcomes below makes advantage of linear covariate-adjustment for the baseline of the outcome, the primary endpoint can equivalently be regarded to be each participant's 12-month measurement. This is convenient because then those with a 12- month outcome, but whose baseline measurement is missing, are not regarded to be missing the endpoint. The primary outcome is therefore operationalised within the statistical model as the 12-month body weight, rather than the change in this from baseline to 12 months. It is not thought that this outcome will be missing at baseline, as it is involved in eligibility criteria and is a minimisation factor. This approach may be more useful for other outcomes. The primary outcome will be analysed using a repeated measures ANCOVA via a linear mixed effects (LME) model incorporating the 3 post-baseline measurements of the body weight (2, 6 and 12 months). All outcome measurement from all randomised subjects who provide at least one post-baseline valid measurement will

This mixed model will include fixed effect terms for arm (1 parameter), centre (1 parameter), sex (1 parameter), age (1 linear parameter), BMI within ethnicity (3 parameters), whether or not subjects volunteer to take part in the sub study (1 parameter), "time" (2 parameters), the baseline of the outcome (continuous body weight -1 parameter) and its missing indicator required for the missing indicator method (1 parameter , if needed) (20). Additionally, the model will include a fixed effect to indicate whether the primary outcome was measured by the participant at each timepoint. The other effects to be included in the model will be the interactions between "time" and each of the other fixed effects in the model (20 parameters). This model allows the treatment effect to be formally tested, at the primary timepoint of 12 months, and estimated at 2 and 6 months. Age is included because this was found to predict drop-out in a related trial (21).

Models will be fitted using a restricted maximum likelihood estimation using an unstructured variancecovariance matrix for the within-subject residuals (since there are only three follow-up timepoints, and so there is a manageable enough number of covariance parameters to expect this type of matrix to be supported by the sample size).

Model assumptions will be checked through the examination of the residuals and other diagnostic plots. Their distribution will be checked to see if there may be any evidence of large departures from a normal distribution, and to understand any influence of outliers (as explained above). It is highly unlikely that the distributional assumption would not be met for the purpose of estimating the parameters, as other studies of a similar sample size with primary outcome of body weight have reported analyses that did not require transformation or non-parametric approaches such as the Bootstrap (21).

In the event of data entry errors occurring in the randomisation (subjects entered in the wrong category of a minimisation factor), the corrected baseline category will be used in the analysis. Moreover, if other model assumptions do not hold such as model not converging, we will follow the steps written in section 8.2.

7.2.2 Primary estimand

Recently there has been a new guideline about strategies on how to deal with events occurring in the middle of the trial and how these relate to the treatment effect that reflects the clinical question posed by a clinical trial objective(10).

The following primary estimand, defined by its five attributes, is then considered:

Attributes of the estimand¹:

1 Population of interest: Described in section 5.0 (see ITT trial sample)		ble)	
2 Varia	ble (endpoint) of interest: D	Described in section 6.1	
3 Treatr	nent of interest:	Described in section 2.3	
4 Interc	urrent events ² :		Strategy ³ for addressing the
			intercurrent event:
a)	Death		Treatment policy
b)	Pregnancy/ Treatment discon	ntinuation due to pregnancy	Hypothetical strategy
c)	Concomitant treatment: Eg.	weight loss program /bariatric surgery/	Treatment policy;
	gym personal trainer		
d)	Development of an illness, s	ay cancer or COVID-19 or other	Treatment policy [†]
	disease/AE that affects a par	ticipants' weight	
e)	Treatment discontinuation d	ue to an AE not affecting participants	Treatment policy
,	weight		1 0
f)	Treatment discontinuation d	Treatment policy	
g)	() Treatment discontinuation due to run out of supply Treatment policy		
h)	Treatment discontinuation due to being indirectly affected by		
	COVID-19 (preventing from	coming to clinical visits)	1 2
	· · · · · · · · · · · · · · · · · · ·	o · · · · · · · · · · · · · · · · · · ·	

5 Population-level summary for the variable: Difference in weight gain between those taking IPE and control inulin after 12 months

¹Citing the ICH E9-R1, "An estimand is a precise description of the treatment effect reflecting the clinical question posed by a given clinical trial objective"(10).

²Intercurrent events are: "Events occurring after treatment initiation that affect either the interpretation or the existence of the measurements associated with the clinical question of interest.(...) Unlike missing data, intercurrent events are not to be thought of as a drawback to be avoided in clinical trials" (10).

³This is the specification of how to account for the intercurrent events that reflect the scientific question of interest. To note is that *'clarity in the estimand gives a basis for planning which data need to be collected and hence which data, when not collected, present a missing data problem to be addressed in the statistical analysis'*(10).

⁺This will be followed by a hypothetical strategy as sensitivity analysis.

To summarize, the treatment policy strategy (where the value of a subject's weight will used regardless of whether the intercurrent event occurred) will be used for all intercurrent events apart from pregnancy, where a hypothetical strategy will be considered (10). This means that we are not interested in the weight after a woman gets pregnant (since weight is evidently changed after pregnancy), but only in the 'hypothetical' weight had the subject not become pregnant. Therefore, the weight after a subject is known to be pregnant will not be considered for the ITT analysis, but we will make use instead of the linear mixed effects model which will indirectly impute the 'missing' data (see next section).

7.2.3 Missing data

An expert missing-data group concluded that rather than statisticians reacting to missing data at the end of a trial, there should be comprehensive, proactive planning for handling missing data at the stage of designing trials (22). The group recommended there should be consideration of missing data mechanisms (e.g Missing At Random), and, if the missing data may be informative that appropriate sensitivity analyses should be undertaken to investigate the robustness of the inferences to the different assumptions made by the main analysis.

It is anticipated that there may be approximately 25% missing data at the 12-month timepoint. The linear mixed effects model, above, will assume that the missing data is "missing at random" (MAR). This is an advantage over the assumption that the missing data is "missing completely at random" because it corrects for contribution to missing data from the covariates in the model and the correlated body weight outcome over time. The robustness to this assumption will be challenged using the sensitivity analyses. Multiple imputation is an alternative approach that also makes a MAR assumption, however we will use the likelihood approach of the linear mixed effects model, above, that gives similar resulting estimates (23).

7.2.4 Sensitivity analysis to missing data – 'Tipping point' analysis

A sensitivity analysis will be undertaken to assess the possibility of alternative plausible values of treatment effect arising from potential mishandling of missing data in the primary analysis model. The LME model for the primary outcome analysis described above is the first of a two-part approach called the Intention to Treat Strategy (16) in which a second analysis examines the sensitivity of the results to missing data in the full randomised, Intention to Treat, population. This meets the ideal of ITT to include everyone randomised. The approach to missing data follows the recently published implementation paper of the ITT strategy (23).

For the sensitivity analysis, we pre-specify a range for body weight from -5kg to +5kg over which the mean of the "unobserved outcome data" might depart (or be different) from the mean of the "observed outcome data" (23). In terms of a typical individual subject with unobserved (i.e. missing) data, this range can be thought of as the amount by which s/he may on average have had a different estimated treatment effect compared to the corresponding subject with the outcome data observed (given the same baseline covariates and follow-up data in the LME model). The range (-5 to +5) is chosen to represent both negative and positive departures that could potentially arise as the "net effect" of alternative reasons which may be unknown; such as dropout due to no anticipated further improvement, or dropout due to no improvement so far together with no anticipated achievable improvement. This range of 10Kg (from -5 to +5) is set generously wide for exploring sensitivity of the main results to departures from the MAR assumption, because 5kg (as the maximum departure in either direction) is larger than the detectable between-arm treatment effect of 2kg seen in superiority trials (difference in means) which is a sizeable shift in the mean of the distribution for dropouts compared to completers.

At the end of the trial, the fractions of individuals with missing data for body weight at 12 months will be available in each arm fi (for intervention) and fc (for control). The parameter representing excess weight in those with unobserved data compared to those with observed data, δ , will take values by passing across the range -5 to +5. Three scenarios will be undertaken within the sensitivity analysis (23, 24). These reflect whether departures from the MAR assumption apply within the intervention arm only (IPE), within the control arm only (inulin), or within both arms equally and in the same direction (thereby potentially cancelling out across the sensitivity range, if the dropout rate were to be the same in both arms).

Scenario 1: the treatment effect from the LME model will be increased by fi δ

Scenario 2: the treatment effect from the LME model will be increased by -fc δ

Scenario 3: the treatment effect from the LME model will be increased by $(fi-fc)\delta$

The number of kg within the range of -5kg to +5kg at which the results change in their statistical significance will be determined (if there is such a number), and this is known as the tipping point. This approach has been used in a recent trial (LEAVO) (25).

7.2.5 Sensitivity analysis for the primary estimand where a hypothetical strategy is adopted for the intercurrent events: AE or concomitant treatments affecting participants' weight

For participants who have a disease such as cancer, COVID-19 or another disease/AE that affects (directly or indirectly) a person's weight, or who starts a diet program/gym personal trainer or something similar, a hypothetical strategy could be an alternative, where we would just be interested in estimating the treatment effect of IPE had these events not happened. Thus, in this sensitivity analysis, measurements occurring after these events will instead be removed from the analysis and the LME model refitted (as done for pregnancy).

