4.2. Treatment Groups

The trial is randomised with two arms and with equal allocation of participants in a 1:1 ratio to these arms. **Active Arm**: IPE for 12 months; **Placebo Arm**: Inulin for 12 months.

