4.5. Sample Size

On the basis outlined below, a sample size of 270 randomised participants (135 per arm) was chosen to provide 90% power to detect a 2kg difference between arms in mean body weight change over 12 months using a two-sided 5% significance test, assuming a 4.35kg SD and with 25% dropout allowance.

Determination of the primary outcome effect size:

In the randomised proof of concept trial, the difference between arms in the change in body weight over 24 weeks was 1.4kg (95% CI: -0.3 to 3.1), p=0.099. Using a Bayesian method recommended for preliminary trials in which evidence in the 95% CI is translated into probabilities, there was a 95% posterior probability of an underlying positive between-arm difference favouring the intervention (11). The posterior probability of intervention-favouring differences greater than 1kg, than 1.5kg, and 2kg were respectively 69%, 47% and 25% based on 24-week intervention. The difference increased in magnitude through successive 8-week, 16-week, and 24-week timepoints. By 24 weeks there were significant reductions in the proportion of intervention participants gaining \geq 3%, and \geq 5% of body weight from a mean baseline of 90kg. We therefore chose a 2kg between-arm 12-month effect size.

Determination of the primary outcome variability:

The chosen detectable effect size of 2kg agreed with that in a weight gain prevention trial conducted over 9 months in young adults (12) by also aiming to detect a 2kg effect, and achieved 4.3kg with 81% retention. The pooled standard deviation (SD) for body weight change was 4.35kg.

Power to detect the effect:

We set a 90% power to detect the primary outcome effect size of 2kg.

Determination of the sample size based on the primary outcome:

The sample size was set to be **270 participants, 135 per arm**. This involves a 25% allowance loss of 12-month primary outcomes, and two-sided statistical testing at the 5% significance level, implying that 202 subjects are required to be followed up with a valid primary outcome. Further adjustment for baseline body weight is expected to improve the precision of the estimated treatment effect.

Power calculation for Mechanistic outcomes:

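### The tipping-point analysis leaves out opposite-direction departures in the two arms, and its range is justified before scaling by the missing fraction, so at 25% missing per arm it can shift the effect by at most 1.25 kg

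*SAP*

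**What the plan says.** Section 7.2.3 states: "It is anticipated that there may be approximately 25% missing data at the 12-month timepoint". The flow diagram in section 7.1.5 expects 101 of 135 followed up in each arm, so the plan's working assumption is about 25% missing in both.

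Section 7.2.4 defines δ as the excess weight of those with unobserved data over those with observed data and passes it from −5 to +5 kg. Departures from missing at random (MAR) may lie "within the intervention arm only (IPE), within the control arm only (inulin), or within both arms equally and in the same direction". With fi and fc the missing fractions in the IPE and inulin arms, the effect from the mixed model is moved by fi·δ (Scenario 1), −fc·δ (Scenario 2) or (fi − fc)·δ (Scenario 3). The section itself notes that Scenario 3 can cancel when dropout is equal. The tipping point is the δ at which statistical significance changes.

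The range, according to the same section, "is set generously wide for exploring sensitivity of the main results to departures from the MAR assumption", on the ground that 5 kg is larger than the 2 kg between-arm effect the trial is designed to detect.

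**The concern.** Two things stand out.

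First, the only scenario that moves both arms moves them together. Under the plan's own expectation of equal dropout it does nothing. The combination that moves the effect most, δ in one arm and −δ in the other, is absent.

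Second, the argument for the width of the range mixes scales. Five kilograms is a shift among the missing quarter of an arm; 2 kg is a difference between whole-arm means. The two become comparable only after the 5 kg is multiplied by the missing fraction, as the section's own formulas do.

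At stake is how far a positive result can be called robust. Section 7.2.4 is the only planned analysis of the primary outcome that departs from MAR. Section 7.2.5 removes measurements and refits the same model, and the complier analysis in section 7.7.1 also rests on MAR. A statement that no tipping point was found will therefore carry weight, and it should reflect the full range of departures that the plan calls wide.

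**Working it through.** **Inputs, all from the SAP.** Section 4.5: "The pooled standard deviation (SD) for body weight change was 4.35kg"; "We therefore chose a 2kg between-arm 12-month effect size"; "We set a 90% power to detect the primary outcome effect size of 2kg"; "two-sided statistical testing at the 5% significance level". Section 4.2: "equal allocation of participants in a 1:1 ratio to these arms". Sections 7.1.5 and 7.2.3: 101 per arm followed up, about 25% missing. Section 7.2.4: δ from −5 to +5 kg.

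**The plan's own figure.** n per arm = 2 × (1.960 + 1.282)² × 4.35² / 2² = 99.4, so 100 per arm and 200 in total; 200 / 0.75 = 267. Power with 101 per arm is 90.4%. The stated 202 and 270 are reproduced and are not in dispute.

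**Largest shift at fi = fc = 0.25 and |δ| = 5 kg.**
- Scenario 1: 0.25 × 5 = 1.25 kg
- Scenario 2: 0.25 × 5 = 1.25 kg
- Scenario 3: (0.25 − 0.25) × 5 = 0 kg
- Opposite directions (not planned): (0.25 + 0.25) × 5 = 2.50 kg

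With unequal dropout the largest planned shift rises: 0.30 × 5 = 1.50 kg at 30%/20%, and 0.35 × 5 = 1.75 kg at 35%/15%. The opposite-direction shift stays at 2.50 kg in both cases.

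**Tipping points.** SE = 4.35 × √(2/101) = 0.612 kg, so significance needs 1.96 × 0.612 = 1.20 kg. This SE is unadjusted and is taken not to change with δ. The δ that removes significance is (estimate − 1.20) / 0.25 in one arm, or (estimate − 1.20) / 0.50 per arm in opposite directions. Estimates are sizes of a benefit for IPE.

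| Estimate (kg) | Excess over 1.20 | δ, one arm | δ per arm, opposite | Gap between the arms' dropouts, opposite |
|---|---|---|---|---|
| 2.0 | 0.80 | 3.2 | 1.6 | 3.2 |
| 2.5 | 1.30 | 5.2 (outside range) | 2.6 | 5.2 |
| 3.0 | 1.80 | 7.2 (outside range) | 3.6 | 7.2 |

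The largest estimate that the planned scenarios can tip is 1.20 + 1.25 = 2.45 kg. With an opposite-direction scenario it is 1.20 + 2.50 = 3.70 kg. The two analyses can therefore give different answers for estimates between about 2.45 and 3.70 kg.

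**Sensitivity to the SE.** Section 4.5 expects baseline adjustment to improve precision but gives no figure. If adjustment cut the SE by 30% (an assumption), significance would need 0.7 × 1.20 = 0.84 kg. A 2 kg estimate would then tip at (2 − 0.84) / 0.25 = 4.6 kg in one arm, and the affected window would be 0.84 + 1.25 = 2.09 to 0.84 + 2.50 = 3.34 kg.

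**The case against.** The strongest reply has five parts.

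- **The planned check works where it matters most.** Tipping means losing significance, not cancelling 2 kg. A 2 kg estimate needs a shift of only 0.80 kg, which Scenarios 1 and 2 reach at 3.2 kg. This stands. A reader might infer from 1.25 kg being less than 2 kg that the analysis cannot expose fragility at the design effect, and that would be wrong.
- **A twofold overstatement of robustness is a matter of units.** With equal dropout, 3.2 kg in one arm and 1.6 kg per arm in opposite directions give the same gap between the arms' dropouts and the same shift. Scenarios 1 and 2 thus already cover opposite departures up to 2.5 kg per arm. This also stands. Even as a ratio of maximum shifts, two holds only at equal dropout: it is 2.50 / 1.50 = 1.67 at 30%/20% and 2.50 / 1.75 = 1.43 at 35%/15%. No reported estimate or interval would be wrong. What remains uncovered is 2.5 to 5 kg per arm.
- **The gaps needed are large.** At estimates of 2.5 and 3.0 kg they are 5.2 and 7.2 kg, both above the 4.35 kg SD of weight change. This is a fair caution about plausibility. However, the plan's own one-arm range already admits a 5 kg gap, so the first of these lies barely beyond what it accepts.
- **Nothing in the SAP says that dropouts will depart in opposite directions.** True. A reader might suppose that IPE dropouts regain weight while control dropouts seek other help, but that is speculation. Nor does the SAP give a reason to assume equal departures in the same direction.
- **The formulas are printed openly and attributed to published methods.** They are, so nothing is hidden. The rationale for the range still compares unlike quantities.

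**Conclusion.** The point holds as a modest, inexpensive improvement. Section 7.2.4 omits opposite-direction departures. At 25% missing per arm its largest shift is 1.25 kg, and its argument that the range is wide leaves out the missing fraction. The practical consequence is confined to estimates of about 2.45 to 3.70 kg, for which the report would say that no tipping point exists although departures inside ±5 kg per arm would remove significance. Below that window the existing scenarios suffice.

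The window assumes equal 25% missingness and an SE of 0.612 kg that does not vary with δ; a smaller adjusted SE would move it down. The primary analysis and the sample size are unaffected.

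**What to change.** In section 7.2.4:

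1. Add Scenario 4, with δ in the IPE arm and −δ in the inulin arm, so that the mixed-model effect is increased by (fi + fc)·δ over the same range. Alternatively, present a grid of δ for IPE against δ for inulin.
2. Report its tipping point beside the other three, and state the implied gap between the two arms' dropouts (2δ in Scenario 4) so that plausibility can be judged. Label the extreme, a 10 kg gap, as possibly implausible.
3. Replace the reason given for the range with the shift it produces: f·δ, that is up to 1.25 kg in one arm and 2.50 kg for opposite departures at 25% missing, restated with the observed fractions in the report.

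The cost is one formula, one table row or figure, and an SAP amendment, for which section 1.2 requires at least Trial Steering Committee approval. No new data are needed. The downside is that a positive result may look less robust. The change should be made before unblinding.
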